Statistical Analyses

The original sample size goal was calculated with a power analysis (G*Power 3.1, Faul et al., 2009) and determined to be 48 participants based on a one-tailed independent samples (prepost) *t*-test with an effect size of 0.80, alpha level of .05, and power set at .85. The power level of .85 was deemed sufficient based on the only prior randomized control trial examining the efficacy of BCST that used the LCQ as a primary outcome measure (Chamberlain Mitchell et al., 2016). A large effect size of .80 was chosen as a conservative value which would be advantageous as we planned to run an analysis of covariance (ANCOVA) and not a *t*-test to

analyze LCQ score change. To account for the possible attrition rate of 16.5% reported in a previous study (Chamberlain Mitchell et al., 2016), we had a goal to recruit 56 participants. This sample target size number was modified as the study progressed due to multiple factors, including a shorter than anticipated recruitment timeline related to a funding delay, and interim analyses that showed a large difference in the primary outcome measure between groups.

Analyses were conducted using R-4.4.2 (R Core Team, 2021). Group differences in mean total LCQ and VAS scores from T0-to-T1 and T0-to-T2 were examined, accounting for T0 assessment scores using an ANCOVA. The variance in responses for both LCQ and VAS scores was very high, making it difficult to determine linearity between T0 and T1 and T2 scores. Therefore, an interaction term between the treatment group and T0 score was considered to account for the potential different treatment effects at different T0 scores. All interaction terms were not statistically significant (p = .26, p = .46, p = .95, p = .36) for LCQ at T1, LCQ at T2, VAS at T1, or VAS at T2, respectively, suggesting homogeneity of the regression slopes. Shapiro-Wilk tests suggested insufficient evidence of non-normality of residuals (p = .89, p = .09, p = .29, p = .38). Lastly, Levene's test found no evidence of error variance heterogeneity (p = .30, p = .74, p = .58, and p = .47). Thus, the basic assumptions necessary for the ANCOVA were met.

Results

Thirty-nine individuals with RCC enrolled in the study between July 2023 and June 2024. Twelve participants completed the control treatment (11 women; mean age, 60 years) and 18 completed the IBCST treatment (16 women; mean age, 62 years). One IBCST participant was lost to follow up at T2 and so was not included in T2 analyses.

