Leicester Cough Questionnaire

At T1, 72% of IBCST participants achieved a meaningful improvement in LCQ total score and this increased to 76% at T2. Mean domain and total LCQ scores for both groups during each assessment period are shown in Table 1. Change in mean total LCQ scores from T0-T1 was 3.74 and 0.58, and from T0-T2 was 4.10 and 0.83, for the IBCST and control groups, respectively. ANCOVA analysis revealed mean total LCQ score changes were significantly greater in the IBCST group than in the control group from T0-to-T1 (mean difference between groups = 3.24, 95% CI = 0.72-5.76, standard error = 1.227, p = .014, ηp^2 = 0.205), and T0-to-T2 (mean difference between groups = 3.30, 95% CI = 0.286-6.32, standard error = 1.467, p=0.033, ηp^2 = 0.163).

Cough Severity Visual Analog Scale (VAS)

Mean VAS scores for both groups at each assessment period are shown in Table 1. Change in mean total VAS scores from T0-T1 was -15 and 1, and from T0-T2 was -7 and 7, for the IBCST and control groups, respectively. ANCOVA analysis revealed there was mild evidence of a larger decrease from T0-to-T1 for the IBCST group compared to the control group (mean difference between groups = -16.1, 95% CI= -32.7-0.46, Std error = 8.804, p = .056, $\eta p^2 = 0.128$), with no evidence of a difference in the mean score change from T0-to-T2 (mean difference between groups = -11.73, 95% CI = -28.53-5.06, Std. error = 8.170, p = .338, $\eta p^2 = 0.073$).

Table 1

Mean LCO and VAS Scores

		LCQ				VAS
		Physical	Social	Psych	Total	Total
					(SD)	(SD)
	T0	3.58	2.82	2.64	9.04	49
					(2.76)	(15.97)
IBCST	T1	4.62	4.03	4.13	12.78	33.94
					(3.69)	(21.32)
	T2	4.71	4.22	3.88	13.03	44.18
					(4.3)	(22.85)
	T0	3.67	2.75	2.45	8.87	49.08
					(2.76)	(22.39)
Control	T1	3.74	3.04	2.67	9.45	50.08
					(3.50)	(22.39)
	T2	3.75	3.17	2.79	9.70	56.42
					(4.29)	(23.74)

References

- Birring, S. S., Prudon, B., Carr, A. J., Singh, S. J., Morgan, M. D., & Pavord, I. D. (2003). Development of a symptom specific health status measure for patients with chronic cough: Leicester Cough Questionnaire (LCQ). *Thorax*, 58(4), 339-343. doi:10.1136/thorax.58.4.339
- Chamberlain, S. A., Garrod, R., Douiri, A., Masefield, S., Powell, P., Bucher, C., Pandyan, A., Morice, A. H., & Birring, S. S. (2015). The impact of chronic cough: a cross-sectional European survey. *Lung*, 193(3), 401-408. doi:10.1007/s00408-015-9701-2

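### Two reported VAS statistics contradict their own companion figures: the T2 p-value of .338 should be about .163, and the T1 standard error of 8.804 should be about 8.08

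*Combined protocol and SAP*

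**What the plan says.** The combined document is protocol, analysis description and results in one. Under Statistical Analyses, group differences in LCQ and VAS from T0 to T1 and from T0 to T2 are compared "accounting for T0 assessment scores using an ANCOVA". Under Results, 12 control and 18 IBCST participants completed treatment, and "One IBCST participant was lost to follow up at T2 and so was not included in T2 analyses". That gives 30 participants at T1 and 29 at T2.

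The section on the Cough Severity VAS reports:

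- T0 to T1: "mean difference between groups = -16.1, 95% CI= -32.7-0.46, Std error = 8.804, p = .056", with partial eta-squared 0.128, described as mild evidence of a larger decrease.
- T0 to T2: "mean difference between groups = -11.73, 95% CI = -28.53-5.06, Std. error = 8.170, p = .338", with partial eta-squared 0.073, described as no evidence of a difference.
- Group changes: "Change in mean total VAS scores from T0-T1 was -15 and 1, and from T0-T2 was -7 and 7", IBCST first and control second.

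The LCQ section states the total-score change "from T0-T2 was 4.10 and 0.83, for the IBCST and control groups, respectively". Table 1 gives the group means.

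**The concern.** In an ANCOVA with one group term, the estimate, standard error, confidence interval, p-value and partial eta-squared are tied together: any one follows from the estimate, one other figure and the degrees of freedom. In each VAS result one figure breaks that tie. At T2 a t-ratio of about 1.4 cannot give p = .338. At T1 an interval only about 33 points wide is too narrow for a standard error of 8.804.

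These are the only between-group tests reported for the secondary outcome. Someone who takes the T1 estimate and standard error into a meta-analysis would give the study (8.08/8.804)² = 0.84 of its proper inverse-variance weight. Someone who derives a standard error from the T2 p-value would get about 12.0 instead of 8.17.

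**Working it through.** **Inputs.** Estimates, intervals, standard errors, p-values and partial eta-squared are from the two outcome sections. The model is from Statistical Analyses and the numbers of participants from Results. With intercept, group and T0 score, df = n - 3: 30 - 3 = 27 at T1 and 29 - 3 = 26 at T2. The critical values t(.975) are 2.0518 and 2.0555.

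**Formulas.** t = difference / SE; two-sided p from t on df; CI = difference ± t(.975) × SE, so SE = half-width / t(.975); partial eta-squared = t² / (t² + df).

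**Step 1: reproduce the LCQ results.**

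| | t | p (printed) | CI (printed) | eta² (printed) |
|---|---|---|---|---|
| LCQ T1 | 3.24/1.227 = 2.641 | .0136 (.014) | 0.72 to 5.76 (0.72 to 5.76) | .205 (0.205) |
| LCQ T2 | 3.30/1.467 = 2.249 | .0332 (.033) | 0.285 to 6.315 (0.286 to 6.32) | .163 (0.163) |

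Both agree with print within rounding, which confirms the model and the degrees of freedom.

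**Step 2: VAS T2.**

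- From the SE: t = -11.73/8.170 = -1.436, p = .163, CI -28.52 to 5.06, eta² = .0735.
- From the CI: half-width (5.06 + 28.53)/2 = 16.795; SE = 16.795/2.0555 = 8.171; p = .163.
- From eta² = 0.073: p = .164.
- Rounding of the printed difference and SE moves p only between .1628 and .1632.
- Working back from p = .338: t = 0.976, SE = 11.73/0.976 = 12.02, CI about -36.4 to 13.0, eta² = .035. None of these is printed.

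**Step 3: VAS T1.**

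- From the CI: half-width (0.46 + 32.7)/2 = 16.58; SE = 16.58/2.0518 = 8.08 (8.07 to 8.09 with rounding of the limits).
- From p = .056: SE = 16.1/1.997 = 8.06.
- From eta² = 0.128: SE = 16.1/1.991 = 8.09.
- With the printed 8.804: t = -1.829, p = .079, CI -34.2 to 2.0, eta² = .110. None of these matches print.
- 8.804/8.08 = 1.09.

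The value 8.084, which is 8.804 with two digits exchanged, lies in the supported range. That is a plausible cause, but the documents do not say so and the finding does not depend on it.

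**Step 4: can another convention rescue the printed values?** No. The T2 p is .163 to .164 with df 25 or 27, .151 with a normal reference, .081 one-sided, and .194 if the two VAS standard errors were swapped. The T1 SE from the CI is 8.07 to 8.09 for df 26 to 28, and 8.46 with a normal critical value.

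**Step 5: two lesser mismatches, not shown to be errors of analysis.**

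- *IBCST VAS change at T2.* Stated as -7; Table 1 gives 44.18 - 49 = -4.82. The T0 mean covers 18 people and the T2 mean 17, which may explain it. The LCQ has a similar gap: 13.03 - 9.04 = 3.99 against 4.10 stated. If -7 refers to the 17, their T0 mean is 44.18 + 7 = 51.18, and the lost participant's T0 is 18 × 49 - 17 × 51.18 = 11.9. Because -7 is rounded, that value could be anywhere from about 3 to 20. The adjusted difference then implies a baseline slope of (44.18 - 56.42 + 11.73)/(51.18 - 49.08) = -0.51/2.10 = -0.24 (-0.20 to -0.32), which is unusual but possible. Conversely, positive slopes of 0.3 to 0.8 would need an IBCST T0 mean of 47.4 to 48.4 and a change of about -3.2 to -4.3, so -7 may itself be the misprint.
- *IBCST T2 LCQ row.* The domains sum to 4.71 + 4.22 + 3.88 = 12.81; the printed total is 13.03, a gap of 0.22. The other five rows agree within .01. The raw difference with the printed total, 13.03 - 9.70 = 3.33, sits close to the adjusted 3.30, which makes a domain cell the likelier misprint but does not exclude the total.

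**The case against.** The arithmetic is not in dispute; the case on the other side concerns weight and remedy.

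- *These are reporting slips with little consequence.* T2 is non-significant at .338 or .163, and T1 is above .05 at .056 or .079. A reader who relies on the estimates and intervals is not misled. This stands, and it limits the weight of the point. It does not make the printed figures right.
- *The source of .338 is unknown.* Models with a group-by-T0 interaction were also examined, and .338 may have been copied from another model or coefficient. That is possible, but it does not make .338 the companion of -11.73. It does mean that the replacement should come from the output, with .163 as the expected value.
- *The T2 wording is not made wrong by p = .163.* With an interval from -28.53 to 5.06, a conventional reading of non-significance still holds. This stands: the sentence deserves a second look because it was printed beside .338, but it need not change.
- *The lesser mismatches are not proven errors.* This also stands. Loss of one participant may explain the -7, and either a domain or the total could be wrong in the LCQ row. Both call only for neutral reconciliation.

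**Conclusion.** The concern holds. The VAS T2 p-value should be about .163, so the printed .338 is roughly double what its own estimate and standard error imply. The VAS T1 standard error should be about 8.08, so 8.804 is about 9% too large. In each result, all the other printed figures agree with one another and one figure stands alone.

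This rests on the stated ANCOVA with T0 as covariate and on 30 and 29 analysed participants. The LCQ results confirm both, and one degree of freedom either way changes nothing material. No conclusion at the .05 level changes, and the primary outcome's between-group tests are unaffected. The -7 and the 12.81 against 13.03 remain open queries.

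**What to change.** Check both VAS results against the existing ANCOVA output. Replace the T2 p-value (expected about .163) and the T1 standard error (expected about 8.08), and reread the T2 sentence beside the corrected p-value.

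In the same pass:

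- State on which participants the IBCST VAS T0-to-T2 change was computed. Confirm or correct the -7, and show in Table 1 the n at each visit and the T0 mean of the 17 followed to T2.
- Find which cell of the IBCST T2 LCQ row is wrong, with the total included among the candidates.

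The cost is a correction of reported figures from output that already exists. No new data and no change to design or analysis are needed.
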